**9.5. Appendix E Schedule of Events**

Visit Number	1	2	3	4	5	6	7	8	9	10	USV a
Type of Visit	C	C	C	C	C	SC	C	SC	SC	C	C
Month	CCI										
Timepoint											
Study Visit Day	Screening b										
Window Allowance (Days)	-28	NA	NA	0	±1	-1 to -7 +3	+3 to +5	±5	±5	±5	+14 NA
Days from Last Study Intervention		CCI									
ICF, demographics, concomitant medications, medical history	X	X									
Inclusion/exclusion criteria	X	X									
Physical examination d	X	X									
Vital signs e	X	X									
Pregnancy testing f	X	X									

ModernaTX, Inc.  
Protocol mRNA-CRID-004

Statistical Analysis Plan, Version 2.0  
Date Issued: 27JAN2024

Visit Number	1	2	3	4	5	6	7	8	9	10	USV a
Type of Visit	C	C	C	C	C	SC	C	SC	SC	C	C
Month	CCI										
Timepoint											
Study Visit Day	Screening b										
Window Allowance (Days)	-28	NA	NA	0	±1	-1 to -7 +3	+3 to +5	±5	±5	±5	±14
Days from Last Study Intervention		CCI									
Blood for humoral immunogenicity g		X			X	X	X			X	
CCI											
NP swab for virus detection h		X									X
Randomization		X									

ModernaTX, Inc.  
Protocol mRNA-CRID-004

Statistical Analysis Plan, Version 2.0  
Date Issued: 27JAN2024

Visit Number	1	2	3	4	5	6	7	8	9	10	USV a
Type of Visit	C	C	C	C	C	SC	C	SC	SC	C	C
Month	CCI										
Timepoint											
Study Visit Day	Screening b										
Window Allowance (Days)	-28	NA	NA	0	±1	-1 to -7 +3	+3 to +5	±5	±5	±5	±14
Days from Last Study Intervention		CCI									
Study intervention (including 30-minute postdosing observation period)		X									
eDiary activation for recording solicited ARs (7 days) i		X									
Review of eDiary ARs j					X						
Follow-up safety calls k						X		X	X		

Visit Number	1	2	3	4	5	6	7	8	9	10	USV a	
Type of Visit	C	C	C	C	C	SC	C	SC	SC	C	C	
Month	CCI											
Timepoint												
Study Visit Day	Screening b											
Window Allowance (Days)	-28	NA	NA	0	±1	-1 +3 to +3	-7 +3 to +3	±5	±5	±5	±14	NA
Days from Last Study Intervention		CCI										
Unsolicited AEs l		X	X	X	X	X						
SAEs	X	X	X	X	X	X	X	X	X	X	X	
AESIs, MAAEs, and AEs leading to withdrawal from the study m		X	X	X	X	X	X	X	X	X	X	
Concomitant medications and nonstudy vaccinations m		X	X	X	X	X	X	X	X	X	X	

Abbreviations: AE=adverse event; AESI=adverse event of special interest; AR=adverse reaction; BMI=body mass index; C=clinic; COVID-19=coronavirus disease 2019; D=Day; EoS=end-of-study; eDiary=electronic diary; FDA=Food and Drug Administration; FSH=follicle-stimulating hormone; ICF=informed consent form; M=month; MAAE=medically attended AE; NA=not applicable; NP=nasopharyngeal; SAE=serious adverse event; SC=safety call; USV=unscheduled visit.

Note: In accordance with “FDA Guidance on Conduct of Clinical Trials of Medical Products during COVID-19 Public Health Emergency”[\(DHHS 2020\)](#), Investigators may convert study site visits to telemedicine visits with the approval of the Sponsor.

- a. Participants may experience AEs that necessitate a USV. Additional examinations may be conducted at these visits as necessary to ensure the safety and well-being of participants during the study.
- b. The Screening Visit and Day 1 may be performed on the same day or a different day. Additionally, the Screening Visit may be performed over multiple visits if within the 28-day screening window. If a participant returns for the D1 visit more than 28 days after their Screening Visit for any reason and continues to provide consent to participate in the study, the participant may be rescreened, for study eligibility. All assessments for eligibility must be repeated.
- c. A blood draw will be collected at 6 hours post vaccine injection on D1.
- d. A full physical examination, including height, weight, and BMI will be performed at Screening. Symptom-directed physical examinations may be performed at other timepoints at discretion of the Investigator. On each dosing day before injection, the arm receiving the injection should be examined and the associated lymph nodes should be evaluated. Any clinically significant finding identified by a healthcare professional during study visits should be reported as an MAAE.
- e. Vital signs measurements: Systolic and diastolic blood pressures, pulse rate, respiratory rate, and body temperature. The preferred route of temperature assessment is oral. On the day of vaccination, vital signs will be collected once before vaccination and once at least 30 minutes after vaccination. Vital signs may be collected at other clinic visits in conjunction with a symptom-directed physical examination.
- f. A pregnancy test either via blood or point-of-care urine test will be performed at the Screening Visit and before the vaccine dose on Day 1, if Day 1 is not on the same day as the Screening Visit. At the discretion of the Investigator, a pregnancy test either via blood or point-of-care urine can be performed at any time. If a urine test cannot be confirmed as negative (eg, an ambiguous result), a serum pregnancy test is required. The participant's FSH level may be measured at the Screening Visit, as necessary, and at the discretion of the Investigator, to confirm postmenopausal status.
- g. D1 (Baseline) blood samples for CCI
- h. An NP swab specimen for viral respiratory pathogens will be collected prior to the study intervention administration on Day 1. At USVs participants with symptoms of respiratory tract infection may be tested by NP swab for respiratory viruses at the Investigator's discretion to include influenza, RSV and SARS-CoV-2, which may impact analyses of reactogenicity and immunogenicity.
- i. eDiary entries will be recorded by the participant at approximately 30 minutes after vaccination while at the clinic with instruction provided by study staff. Study participants will continue to record in the eDiary each day, preferably in the evening and at the same time each day, on the day of vaccination and for 6 days following vaccination. Any solicited AR that is ongoing beyond Day 7 will be reported until resolution.
- j. Solicited ARs recorded in the eDiaries that is ongoing beyond 7 days after injection will be followed up by the study site staff at the next scheduled telephone call or at the next study site visit. Any medication recorded in eDiaries that is taken to prevent or treat pain or fever will also be reviewed at this time.
- k. Trained study personnel will call all participants to collect information relating to any MAAEs, AESIs, AEs leading to withdrawal from the study, SAEs, information on concomitant medications associated with those events; receipt of any nonstudy vaccinations; and receipt of any systemic steroids, immunosuppressive therapies (drugs or biologics), immunoglobulins, and/or blood products.
- l. All unsolicited AEs will be recorded starting the day of each study intervention, and through 28 days following each study intervention.
- m. All concomitant medications will be recorded through 28 days after vaccination. All concomitant medications relevant to or for the treatment of the SAE, AESI, MAAE, or AE leading to study withdrawal will be recorded from D1 through EoS. Any nonstudy vaccinations will be recorded from D1 through EoS.

**9.6. Appendix F Internationally Agreed Order for Display of System Organ Class**

1	Infections and infestations
2	Neoplasms benign, malignant and unspecified (incl cysts and polyps)
3	Blood and lymphatic system disorders
4	Immune system disorders
5	Endocrine disorders
6	Metabolism and nutrition disorders
7	Psychiatric disorders
8	Nervous system disorders
9	Eye disorders
10	Ear and labyrinth disorders
11	Cardiac disorders
12	Vascular disorders
13	Respiratory, thoracic and mediastinal disorders
14	Gastrointestinal disorders
15	Hepatobiliary disorders
16	Skin and subcutaneous tissue disorders
17	Musculoskeletal and connective tissue disorders
18	Renal and urinary disorders
19	Pregnancy, puerperium and perinatal conditions
20	Reproductive system and breast disorders
21	Congenital, familial and genetic disorders
22	General disorders and administration site conditions
23	Investigations
24	Injury, poisoning and procedural complications
25	Surgical and medical procedures
26	Social circumstances
27	Product issues

## 9.7. Appendix G Definition of AE of Clinical Interest by SMQ

**Table 5 List of AE of Clinical Interest by SMQ**

AE of Clinical Interest*	Type of MedDRA Query	Broad or Narrow Search	SMQ Search Criteria
Anaphylactic Reaction	SMQ	Algorithm	A or (B and C) or (D and (B or C)), Specified PT and algorithm approach included in Table 6
Angioedema	SMQ	Narrow	Specified PT terms
Cardiac Arrhythmias	SMQ	Narrow	Specified PT terms
Cardiac Failure	SMQ	Narrow	Specified PT terms
Cardiomyopathy	SMQ	Narrow	Specified PT terms
Central Nervous System Vascular Disorders	SMQ	Narrow	Specified PT terms
Convulsions	SMQ	Narrow	Specified PT terms
Demyelination	SMQ	Narrow	Specified PT terms
Embolic and Thrombotic Events	SMQ	Narrow	Specified PT terms
Haematopoietic Cytopenias	SMQ	Narrow	Specified PT terms
Hypersensitivity	SMQ	Narrow	Specified PT terms
Immune-mediated/Autoimmune Disorders	SMQ	Narrow	Specified PT terms
Ischaemic Heart Disease	SMQ	Narrow	Specified PT terms
Noninfectious Myocarditis/Pericarditis	SMQ	Narrow	Specified PT terms
Peripheral Neuropathy	SMQ	Narrow	Specified PT terms
Vasculitis	SMQ	Narrow	Specified PT terms
*Based on MedDRA 26.1			

**Table 6 Algorithm Approach for Anaphylactic Reaction**

The following criteria will be used to determine anaphylactic reaction:

- A term from Category A
- A term from Category B (Upper Airway/Respiratory) and a term from Category C (Angioedema/Urticaria/Pruritus/Flush) that occurred within 24 hours of each other.
- A term from Category D (Cardiovascular/Hypotension) and at least one of the following:

- A term from Category B (Upper Airway/Respiratory) that occurred within 24 hours of each other.
- A term from Category C (Angioedema/Urticaria/Pruritus/Flush) that occurred within 24 hours of each other.

Anaphylactic Reaction		
Category	Scope	PT Search Term
A	Narrow	Anaphylactic reaction
A	Narrow	Anaphylactic shock
A	Narrow	Anaphylactic transfusion reaction
A	Narrow	Anaphylactoid reaction
A	Narrow	Anaphylactoid shock
A	Narrow	Circulatory collapse
A	Narrow	Dialysis membrane reaction
A	Narrow	Kounis syndrome
A	Narrow	Procedural shock
A	Narrow	Shock
A	Narrow	Shock symptom
A	Narrow	Type I hypersensitivity
B	Broad	Acute respiratory failure
B	Broad	Asthma
B	Broad	Bronchial oedema
B	Broad	Bronchospasm
B	Broad	Cardio-respiratory distress
B	Broad	Chest discomfort
B	Broad	Choking
B	Broad	Choking sensation
B	Broad	Circumoral oedema
B	Broad	Cough
B	Broad	Cough variant asthma
B	Broad	Cyanosis
B	Broad	Dyspnoea
B	Broad	Enhanced respiratory disease
B	Broad	Hyperventilation
B	Broad	Irregular breathing
B	Broad	Laryngeal dyspnoea
B	Broad	Laryngeal oedema
B	Broad	Laryngospasm
B	Broad	Laryngotracheal oedema
B	Broad	Mouth swelling
B	Broad	Nasal obstruction
B	Broad	Oedema mouth
B	Broad	Oropharyngeal oedema
B	Broad	Oropharyngeal spasm
B	Broad	Oropharyngeal swelling
B	Broad	Pharyngeal oedema
B	Broad	Pharyngeal swelling

B	Broad	Respiratory arrest
B	Broad	Respiratory distress
B	Broad	Respiratory failure
B	Broad	Reversible airways obstruction
B	Broad	Sensation of foreign body
B	Broad	Sneezing
B	Broad	Stridor
B	Broad	Swollen tongue
B	Broad	Tachypnoea
B	Broad	Throat tightness
B	Broad	Tongue oedema
B	Broad	Tracheal obstruction
B	Broad	Tracheal oedema
B	Broad	Upper airway obstruction
B	Broad	Wheezing
C	Broad	Allergic oedema
C	Broad	Angioedema
C	Broad	Circumoral swelling
C	Broad	Erythema
C	Broad	Eye oedema
C	Broad	Eye pruritus
C	Broad	Eye swelling
C	Broad	Eyelid oedema
C	Broad	Face oedema
C	Broad	Flushing
C	Broad	Injection site urticaria
C	Broad	Lip oedema
C	Broad	Lip swelling
C	Broad	Nodular rash
C	Broad	Ocular hyperaemia
C	Broad	Oedema
C	Broad	Oedema blister
C	Broad	Periorbital oedema
C	Broad	Periorbital swelling
C	Broad	Pruritus
C	Broad	Pruritus allergic
C	Broad	Rash
C	Broad	Rash erythematous
C	Broad	Rash pruritic
C	Broad	Skin swelling
C	Broad	Swelling
C	Broad	Swelling face
C	Broad	Swelling of eyelid
C	Broad	Urticaria
C	Broad	Urticaria papular
D	Broad	Blood pressure decreased
D	Broad	Blood pressure diastolic decreased
D	Broad	Blood pressure systolic decreased
D	Broad	Cardiac arrest
D	Broad	Cardio-respiratory arrest

D	Broad	Cardiovascular insufficiency
D	Broad	Diastolic hypotension
D	Broad	Hypotension
D	Broad	Hypotensive crisis
D	Broad	Post procedural hypotension

## 9.8. Appendix H Severity Grading of Vital Sign

Vital Signs*	Mild (Grade 1)	Moderate (Grade 2)	Severe (Grade 3)	Potentially Life Threatening (Grade 4)
Fever (°C)** (°F)**	38.0 – 38.4 100.4 – 101.1	38.5 – 38.9 101.2 – 102.0	39.0 – 40 102.1 – 104	> 40 > 104
Tachycardia - beats per minute	101 – 115	116 – 130	> 130	ER visit or hospitalization for arrhythmia
Bradycardia - beats per minute***	50 – 54	45 – 49	< 45	ER visit or hospitalization for arrhythmia
Hypertension (systolic) – mm Hg	141 – 150	151 – 155	> 155	ER visit or hospitalization for malignant hypertension
Hypertension (diastolic) – mm Hg	91 – 95	96 – 100	> 100	ER visit or hospitalization for malignant hypertension
Hypotension (systolic) – mm Hg	85 – 89	80 – 84	< 80	ER visit or hospitalization for hypotensive shock
Respiratory Rate – breaths per minute	17 - 20	21 - 25	> 25	Intubation

Note: If the vital sign results do not meet the criteria for Grade 1-4, they will be treated as Grade 0 for the shift grading table.

\* Participant should be at rest for all vital sign measurements.

\*\* Oral temperature; no recent hot or cold beverages or smoking.

\*\*\* When resting heart rate is between 60 – 100 beats per minute. Use clinical judgement when characterizing bradycardia among some healthy participant populations, for example, conditioned athletes.

## 9.9 Appendix I Imputation Rules for Solicited Adverse Reactions (SARs)

Below are the three scenarios:

1. If the subject does not answer (missing value or shown as “NOT DONE”) for any of the 7 days in eDiary period, then the subject is excluded from the Solicited Safety Set.
2. If the subject has at least one grade 1 or higher SAR for a symptom for a certain day, choose the worst response (or highest grade).
3. If the subject has some days as no symptom and some other days have missing value, set the subject as “NOT DONE”, and categorize it as missing diary partially.

In terms of solicited safety set, if the subject has at least one valid eDiary or Reactogenicity form entry, then this subject will be in the solicited safety set. For scenarios 2 and 3 above, these subjects are included in the Solicited Safety Set.

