8.3.6. Use of Electronic Diaries

At the time of consent, the participants must confirm they will be willing to complete an eDiary (for 7-day reactogenicity). The local and systemic ARs that will be solicited by the eDiary are described in [Table 7](#).

Solicited local and systemic reactogenicity ARs will be collected on the day of each study intervention and during the 7 days after study intervention (ie, the day of dosing and 6 subsequent days). Details on the recording of local and systemic ARs are included in [Section 8.4.6](#).

At each dosing visit, participants will record data into the eDiary starting approximately 30 minutes after dosing under supervision of the site staff to ensure successful entry of assessments. The 30-minute observation period is an opportunity for site staff to train the participant on eDiary completion requirements. The site staff will perform any retraining as necessary.

At each dosing visit, participants will be instructed or reminded on thermometer usage to measure body temperature, ruler usage to measure injection site erythema (redness) and swelling/induration (hardness), and self-assessment for localized axillary (underarm) swelling or tenderness ipsilateral (on the same) side as the injection arm during the 7 days after study intervention. Daily oral temperature measurement should be performed at approximately the same time each day using the thermometer provided by the site staff.

The participant will be trained on how to complete the eDiary questions according to the SoA ([Table 1](#)) and also reminded to call the site immediately if they experience any new signs or symptoms.

If a participant does not respond to the eDiary questions according to the SoA, site staff will follow-up with the participant.

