8.4.6. Solicited Adverse Reactions

Solicited ARs are a subset of AEs consisting of selected signs and symptoms that participants are asked to record/report. In this study, the solicited ARs are reactogenicity events. The term “reactogenicity” refers to the occurrence of transient adverse effects associated with vaccine administration. The eDiary will solicit daily participant reporting of ARs using a structured checklist. Participants will record such occurrences in the eDiary on the day of each study vaccine injection and 6 subsequent days.

Severity grading of reactogenicity will occur automatically based on participant entry into the eDiary according to the grading scales presented in [Appendix 3 \(Section 10.3.5\)](#), which are modified from the Toxicity Grading Scales for Healthy Adult and Adolescent Volunteers Enrolled in Preventative Vaccine Clinical Trials ([DHHS 2007](#)). All solicited ARs (local and systemic) will be considered causally related to dosing.

Any solicited AR that meets any of the following criteria must be entered into the participant's source document and must also be recorded by the study site staff in the EDC where reactogenicity is collected:

- Solicited local or systemic ARs that were not recorded in the eDiary but reported to the study site/Investigator and is Grade 1 or greater.
- Solicited local or systemic AR that results in a visit to a healthcare practitioner including USVs at the study site (MAAE).
- Solicited local or systemic AR leading to the participant withdrawing from the study or the participant being withdrawn from the study by the Investigator (AE leading to discontinuation).
- Solicited local or systemic AR lasting beyond 7 days postinjection.
- Solicited local or systemic AR that leads to participant discontinuation from study intervention.
- Solicited local or systemic AR that otherwise meets the definition of an SAE ([Section 10.3.2](#)).

If a participant reports a solicited AR with onset during the solicited period, but they did not record the event in the eDiary, then the event should be recorded by study staff in the EDC where reactogenicity is collected.

If the event starts during the solicited period, but continues beyond 7 days after dosing, the participants should notify the site to provide an end date and close out the event in the EDC where reactogenicity is collected.

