9.4. Analysis Sets

Analysis sets are listed in [Table 5](#).

Table 5: Analysis Sets

Participant Analysis Set	Description
Randomization Analysis Set	The Randomization Analysis Set consists of all participants who are randomized.
FAS	The FAS consists of all randomized participants who receive the study intervention. Participants will be included in the study arm to which the participant is randomized.
PPS for Immunogenicity	The PPS consists of all participants in the FAS who comply with the injection schedule, comply with the timing of immunogenicity blood sampling to have a Baseline (D1) and at least 1 postinjection assessment, and have no major protocol deviations which impact the immune response. The PPS will be used as the primary analysis set for analyses of immunogenicity unless otherwise specified.
Safety Set	Safety Set consists of all participants who receive one dose of study intervention. The Safety Set will be used for all analyses of safety except for the solicited ARs. Participants will be included in the study arm corresponding to the study intervention that they actually received.
Solicited Safety Set	The Solicited Safety Set consists of all participants in the Safety Set who contribute any solicited AR data. The Solicited Safety Set will be used for the analyses of solicited ARs. Participants will be included in the treatment group corresponding to the study intervention that they actually received.

Abbreviation: AR=adverse reaction; D=day; FAS=full analysis set; PPS=per protocol set.

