#### **6.3.2. Solicited Adverse Reactions**

An AR is any AE for which there is a reasonable possibility that the test product caused the AE. The term “Solicited Adverse Reactions” refers to selected signs and symptoms occurring after injection administration during a specified post-injection follow-up period

(day of injection and 6 subsequent days). The solicited ARs are recorded by the participant in eDiary. The occurrence and intensity of selected signs and symptoms is actively solicited from the participant during a specified post-injection follow-up period (day of injection and 6 subsequent days), using a pre-defined checklist in the eDiary (i.e., solicited ARs). Any solicited ARs occurring within 7 days after injection, if not entered in the eDiary in the required input time window, should be reported in the Reactogenicity eCRF. Solicited ARs reported in both the eCRF and eDiary will be included in the evaluation of solicited ARs.

The following local ARs will be solicited: pain at injection site, erythema (redness) at injection site, swelling/induration (hardness) at injection site, and axillary (underarm) swelling or tenderness ipsilateral to the side of injection.

The following systemic ARs will be solicited: headache, fatigue, myalgia (muscle aches all over the body), arthralgia (joint aches in several joints), nausea/vomiting, chills, and fever.

The solicited ARs will be graded based on the grading scales presented in Table 7 in the protocol, modified from the Toxicity Grading Scale for Healthy Adult and Adolescent Volunteers Enrolled in Preventative Vaccine Clinical Trials ([DHHS 2007](#)). Investigator will assess Grade 4 events (with exception of fever).

If a participant reports a solicited AR with onset during the solicited period, but they did not record the event in the eDiary, then the event should be recorded by study staff in the EDC where reactogenicity is collected.

If a solicited local or systemic AR continues beyond 7 days post injection, the participant should notify the site to provide an end date and close out the event in the EDC where reactogenicity is collected.

All solicited ARs (local and systemic) will be considered causally related to injection.

All solicited ARs analyses will be based on Solicited Safety Set and will be provided by treatment group, unless otherwise specified.

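### SAP Appendix I both excludes and includes a participant with an empty eDiary and a Reactogenicity form entry; scenario 1 needs one added clause

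*SAP*

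**What the plan says.** SAP Appendix I lists three scenarios for solicited reaction data and ends with a paragraph on set membership.

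- Scenario 1: where no answer is given (missing or NOT DONE) "for any of the 7 days in eDiary period, then the subject is excluded from the Solicited Safety Set".
- Closing paragraph: "if the subject has at least one valid eDiary or Reactogenicity form entry, then this subject will be in the solicited safety set".
- Last sentence: "For scenarios 2 and 3 above, these subjects are included in the Solicited Safety Set". Scenario 1 is not named there.

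Three other places bear on membership:

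- Protocol section 9.4, Table 5: "The Solicited Safety Set consists of all participants in the Safety Set who contribute any solicited AR data".
- SAP section 6.3.2, on sources: "Solicited ARs reported in both the eCRF and eDiary will be included in the evaluation of solicited ARs".
- SAP section 6.3.2, on the analysis set: "All solicited ARs analyses will be based on Solicited Safety Set".

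Protocol section 8.4.6 requires site staff to record solicited reactions "that were not recorded in the eDiary but reported to the study site/Investigator and is Grade 1 or greater". The plan therefore foresees records that exist on the form and not in the diary.

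**The concern.** A participant with no eDiary answers but one form entry meets the exclusion rule and the inclusion rule at once. The set concerned carries the first primary endpoint, solicited local and systemic reactions through 7 days. Its membership should not depend on which sentence a programmer follows.

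Falling back on the protocol does not settle the matter. SAP section 1 says the SAP prevails where its methods differ from the protocol's. SAP section 7, which lists changes from the protocol, mentions none for this set, so nothing suggests that a departure from Table 5 was intended.

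Under Protocol section 8.4.6, a reaction recorded because it was missed in the diary is Grade 1 or greater. The participant at issue therefore has a known reaction, and exclusion discards it.

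**Working it through.** **Text comparison**

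| Participant's data | Scenario 1 | Closing paragraph | Protocol Table 5 |
|---|---|---|---|
| No eDiary answer, no form entry | out | out | out |
| No eDiary answer, form entry | **out** | **in** | in |
| Partly completed eDiary | not covered (scenario 3: in) | in | in |

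Only the middle row conflicts.

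**Size**

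The plan gives no figure on this point, so there is none to reproduce. The arm sizes, 30 and 60, are from Protocol Table 4. All event counts below are assumptions. Let N be the arm size including one form-only participant, and x the number with the event among the other N − 1.

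*Event the participant had.* The rate is x/(N − 1) under scenario 1 and (x + 1)/N under the closing paragraph. The difference is (1 − p)/N, with p = x/(N − 1). It is largest at x = 0, where it equals 1/N, and it is zero when p = 1.

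*Event the participant did not have.* The rate is x/(N − 1) under scenario 1 and x/N under the closing paragraph. Scenario 1 is higher by p/N, which also cannot exceed 1/N.

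The bound in either direction is therefore 1/30 = 3.3 points or 1/60 = 1.7 points.

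Grade 3, if the form-only participant had a Grade 3 reaction (Clopper-Pearson 95% CI):

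| Arm | Scenario 1 | Closing paragraph | Difference (points) |
|---|---|---|---|
| 30 | 0/29 = 0.0% (0.0 to 11.9) | 1/30 = 3.3% (0.1 to 17.2) | 3.3 |
| 30 | 1/29 = 3.4% (0.1 to 17.8) | 2/30 = 6.7% (0.8 to 22.1) | 3.2 |
| 30 | 2/29 = 6.9% (0.8 to 22.8) | 3/30 = 10.0% (2.1 to 26.5) | 3.1 |
| 60 | 0/59 = 0.0% (0.0 to 6.1) | 1/60 = 1.7% (0.0 to 8.9) | 1.7 |
| 60 | 2/59 = 3.4% (0.4 to 11.7) | 3/60 = 5.0% (1.0 to 13.9) | 1.6 |

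Any solicited reaction, at assumed rates of about 50%, 70% and 90% in the rest of the arm:

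- Arm of 30: 14/29 = 48.3% versus 15/30 = 50.0%; 20/29 = 69.0% versus 21/30 = 70.0%; 26/29 = 89.7% versus 27/30 = 90.0%. Differences 1.7, 1.0 and 0.3 points.
- Arm of 60: 30/59 = 50.8% versus 31/60 = 51.7%; 41/59 = 69.5% versus 42/60 = 70.0%; 53/59 = 89.8% versus 54/60 = 90.0%. Differences 0.8, 0.5 and 0.2 points.

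Opposite direction, arm of 30. If the form-only participant had only a Grade 1 headache and two others had Grade 3 reactions, the Grade 3 rate is 2/29 = 6.9% under scenario 1 and 2/30 = 6.7% under the closing paragraph. Scenario 1 is 0.2 points higher.

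**How often**

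The documents give no frequency. If 0.1%, 0.5% or 1% of participants were form-only (pure assumption), 270 × f gives 0.3, 1.4 or 2.7 participants. The chance that a given arm of 30 has at least one, 1 − (1 − f)^30, is 3%, 14% or 26%. Protocol section 8.3.6 points to the low end, because "participants will record data into the eDiary starting approximately 30 minutes after dosing under supervision of the site staff".

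**The case against.** The best defence is that the appendix can be read without conflict. The phrase about the eDiary period may name the 7-day window and not the data source, so that not answering means no response from anywhere. A form-only participant with a Grade 1 or higher reaction also fits scenario 2, which names no source and is expressly included. The closing paragraph then addresses membership directly and names the form. On this view a programmer has several consistent statements against one loose line. In addition, the text of SAP section 5.3, which defines this set, is not readable in the public copy and may settle the matter.

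Much of this stands as evidence of intent: inclusion is clearly meant. It does not remove the conflict. If form-only participants fit scenario 2, they still also fit scenario 1 as worded, and no precedence is stated. Section 5.3 might say which rule governs, but the two sentences in Appendix I would still disagree.

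Three stronger readings might be inferred, and the documents support none of them:

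- *Any single missed day excludes a participant.* Scenario 3 and the last sentence of the appendix keep partly completed diaries in the set, so scenario 1 can only mean that no day was answered.
- *The error can only understate reactogenicity.* That holds for any solicited reaction and for the reaction and grade the participant had. SAP section 6.3.2 also tabulates individual reactions by grade, and rates of events the participant did not have move up.
- *The primary safety result is at risk.* Supervised first entry and site follow-up of non-response make form-only participants rare, and Protocol section 9.2 states that no formal hypotheses are tested.

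**Conclusion.** The inconsistency is real and confined to one kind of participant: no eDiary answer and at least one Reactogenicity form entry. Scenario 1 is the sentence out of line with the closing paragraph, Protocol Table 5 and SAP section 6.3.2.

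For one such case, the rates of any solicited reaction and of what the participant experienced fall by at most 3.3 points in an arm of 30 and 1.7 points in an arm of 60, with no change if the rate is already 100%. Rates of events the participant did not have rise, only slightly when those events are uncommon. The bounds follow from the arm sizes alone; the counts and frequencies used as illustrations are assumptions. The most visible effect would be a sole Grade 3 case vanishing from an arm (0/29 instead of 1/30), with widely overlapping intervals. Few or no participants are likely to be affected, and no conclusion is likely to change. This is a minor correctness fix.

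**What to change.** Reword scenario 1 along these lines: *A subject with no valid eDiary answer on any of the 7 days (every day missing or NOT DONE) and with no Reactogenicity form entry is left out of the Solicited Safety Set.*

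This brings scenario 1 into line with the closing paragraph and Protocol Table 5, and removes the loose wording about the 7 days. Check at the same time that SAP section 5.3 agrees.

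The cost is one clause of SAP text, with no change to data collection or table shells. One consequence should be accepted knowingly: the form is described as a place for reactions, so participants who enter the set through it will have at least one reaction. With so few expected, that is a small price for not discarding known events.

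No change to scenario 3 is needed for this point.
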